9.5.1.5 Safety Assessments

Safety assessments are shown in Table 5 (Schedule of Procedures/Assessments) and below.

Safety assessments include monitoring and recording all AEs, including all grading of Common Terminology Criteria for Adverse Events (CTCAE) v4.03, and SAEs; regular

Eisai Confidential Page 45 of 71

laboratory evaluation for hematology, blood chemistry, and urine values; and periodic measurement of vital signs, electrocardiograms (ECGs), ECOG-PS, and physical examinations.

9.5.1.5.1 ADVERSE EVENTS

An AE is any untoward medical occurrence in a patient. An AE does not necessarily have a causal relationship with the medicinal product. For this study, the study drug is tazemetostat.

The criteria for identifying AEs in this study are:

- Any unfavorable and unintended sign (including an abnormal laboratory finding), symptom, or disease found after the time of informed consent, whether or not considered related to the investigational product (Note: Every sign or symptom should not be listed as a separate AE if the applicable disease [diagnosis] is being reported as an AE)
- Any new disease or exacerbation of an existing disease. However, worsening of the primary disease should be captured under efficacy assessments as disease progression rather than as an AE.
- Any deterioration in protocol-required and nonprotocol-required measurements of a laboratory value or other clinical test (eg, ECG or x-ray) that results in symptoms, a change in treatment, or discontinuation of study drug
- Recurrence of an intermittent medical condition (eg, headache) not present pretreatment (Baseline)
- An abnormal laboratory test result should be considered an AE if the identified laboratory abnormality leads to any type of intervention, withdrawal of study drug, or withholding of study drug, whether prescribed in the protocol or not

All AEs, regardless of relationship to study drug or procedure, should be recorded beginning from the time the subject signs the study ICF through the final observation visit. When subject needs to receive other anti-tumor therapy within 30 days after the final study drug administration, final observation must be conducted before initiation of other anti-tumor therapy. SAEs will be collected until the final observation visit.

Any laboratory abnormality considered to constitute an AE should be reported on the CRF. Abnormal laboratory values should not be listed as separate AEs if they are considered to be part of the clinical syndrome that is being reported as an AE. It is the responsibility of the investigator or subinvestigator to review all laboratory findings in all subjects and determine if they constitute an AE. Medical and scientific judgment should be exercised in deciding whether an isolated laboratory abnormality should be classified as an AE.

Abnormal ECG (QTcF) results, if not otherwise considered part of a clinical symptom that is being reported as an AE, should be considered an AE if the QTcF interval is more than 450 ms and there is an increase of more than 60 ms from baseline. Any ECG abnormality that the investigator considers as an AE should be reported as such.

All AEs must be followed until last visit for final observation or until resolution, whichever comes first. When subject needs to receive other anti-tumor therapy within 30 days after the

Eisai Confidential Page 46 of 71

final study drug administration considering the deterioration of subject's physical condition, final observation must be conducted before initiation of other anti-tumor therapy. All SAEs must be followed to resolution or, if resolution is unlikely, to stabilization. For subjects who withdraw from the study and continuously use commercial tazemetostat, all AEs will be followed until discontinuation visit.

Every effort must be made by the investigator or subinvestigator to categorize each AE according to its severity and its relationship to the study treatment.

Assessing Severity of Adverse Events

Adverse events will be graded on a 5-point scale according to CTCAE v4.03. Investigators will report CTCAE grades for all AEs (for both increasing and decreasing severity).

Assessing Relationship to Study Treatment

Items to be considered when assessing the relationship of an AE to the study treatment are:

- Temporal relationship of the onset of the event to the initiation of the study treatment
- The course of the event, especially the effect of discontinuation of study treatment or reintroduction of study treatment, as applicable
- Whether the event is known to be associated with the study treatment or with other similar treatments
- The presence of risk factors in the study subject known to increase the occurrence of the event
- The presence of nonstudy, treatment-related factors that are known to be associated with the occurrence of the event

Classification of Causality

The relationship of each AE to the study drug will be recorded on the CRF in response to the following question:

Is there a reasonable possibility that the study drug caused the AE?

Yes (related) A causal relationship between the study drug and the AE is a reasonable possibility.

No (not related) A causal relationship between the study drug and the AE is not a reasonable possibility.

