9.5.2 Schedule of Procedures/Assessments

9.5.2.1 Schedule of Procedures/Assessments

Table 5 presents the schedule of procedures/assessments for the study.

Eisai Confidential Page 51 of 71

Table 5 Schedule of Procedures/Assessments in Study E7438-J081-206 (EZH-206)

Phase		Due tweetment			Тиол	t-mont		Falls	
rnase		Pre-treatment		Treatment				Follow-up	
Period	Screening 1	Screening 2 ^a	Baseline	Cyc	ele 1	Cycle 2	and later	Discontinuat ion	Final observation
Day		Within 28 days before admin	Within 3 days before admin	1	15 (±3)	1 (±3)	15 ^k (±3)	(+7)	30 days after last dosing (+7) ^{b, 1}
IC for EZH2 gene mutation test	X								
Archival tumor sample submission	X								
IC for study treatment ^c		X							
Demographic data	$[X]^d$	X							
Inclusion/exclusion Criteria		X	X						
Enrollment		X							
Medical history/Current medical condition		X							
Previous therapy		X							
Height		X							
Body weight		X	X		X	X	X	X	X
Physical examination		X	X		X	X	X	X	X
Vital signs		X	X		X	X	X	X	X
ECOG performance status		X	X			X		X	
12-lead ECGs		X	X		X	X	X	X	
Pregnancy test (if applicable)		X						X	
Virus test		X							
Hematology ^j		X	X		X	X	X	X	X
Blood chemistry		X	X		X	X	X	X	X
Urinalysis		X	X		X	X	X	X	X
PK blood sampling ^e					X	[X]			
Tumor assessments (CT/endoscopy) ^f		X				[3	X]	X	
Tumor assessments (PET) ^g		X				[3	X]		
Bone marrow examination (bone marrow aspiration or biopsy) ^h		X				[3	X]		
Tazemetostat administration ⁱ		Continuous 28-day cycle of twice daily (BID)							
Adverse events		From informed consent for study treatment to final observation							
Concomitant drug/therapies From informed consent for study treatment to final observation									

Eisai Confidential Page 52 of 71

Note, [X]: In case to perform.

admin = administration, BID = twice daily, C#D# = Cycle # Day #, CR = complete response, CT = computed tomography, ECG = electrocardiogram, ECOG-PS = Eastern Cooperative Oncology Group-Performance Status, IC = informed consent, PET = positron emission tomography, PK = pharmacokinetics.

- a: Screening 2 assessments may be used as baseline assessments if performed within 3 days of the first administration of study drug.
- b: When subject needs to receive other anti-tumor therapy within 30 days after the final study drug administration, final observation must be conducted before initiation of other anti-tumor therapy and the data within 7 days before next anti-tumor therapy can be used for final observation.

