9.7.1.8.2 ADVERSE EVENTS

The AE verbatim descriptions (investigator terms from the CRF) will be classified into standardized medical terminology using the Medical Dictionary for Regulatory Activities (MedDRA). Adverse events will be coded to the MedDRA lower level term (LLT) closest to the verbatim term. The linked MedDRA preferred term (PT) and primary system organ class (SOC) are also captured in the database.

A treatment-emergent adverse event (TEAE) is defined as an AE that emerges during treatment, having been absent at pretreatment (baseline) or

- Reemerges during treatment, having been present at pretreatment (baseline) but stopped before treatment, or
- Worsens in severity during treatment relative to the pretreatment state, when the AE is continuous.

Eisai Confidential Page 60 of 71 FINAL: 29 Jan 2021

Eisai Confidential Page 61 of 167

Only those AEs that are treatment-emergent will be included in summary tables. All AEs, treatment-emergent or otherwise, will be presented in subject data listings.

The number (percentage) of subjects with TEAEs will be summarized by SOC and PT. A subject will be counted only once within an SOC and PT, even if the subject experienced more than 1 TEAE within a specific SOC and PT. The number (percentage) of subjects with TEAEs will also be summarized by highest CTCAE grade.

The number (percentage) of subjects with treatment-related TEAEs will be summarized by SOC and PT. Treatment-related TEAEs include those events considered by the investigator to be related to study treatment. The number (percentage) of subjects with treatment-related TEAEs will also be summarized by highest CTCAE grade.

The number (percentage) of subjects with SAEs and TEAEs leading to death, discontinuation from study drug, study drug dose reduction or interruption will be summarized by SOC and PT. Subject data listings of all SAEs and AEs leading to death, discontinuation from study drug, study drug dose reduction or interruption will be provided.

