### 5.6.2 Adverse Events

The AE verbatim descriptions (investigator terms from the CRF) will be classified into standardized medical terminology using the Medical Dictionary for Regulatory Activities (MedDRA). AEs will be coded to the MedDRA (Version 22.0) lower level term (LLT) closest to the verbatim term. The linked MedDRA preferred term (PT) and primary system organ class (SOC) will also be captured in the database.

A treatment-emergent adverse event (TEAE) is defined as an AE that emerged during time from the first dose of study drug to 37 days after the subject's last dose, having been absent at pretreatment (Baseline) or

- Reemerged during treatment, having been present at pretreatment (Baseline) but stopped before treatment, or
- Worsened in severity during treatment relative to the pretreatment state, when the AE was continuous.

Only those AEs that are treatment emergent will be included in summary tables. All AEs, treatment emergent or otherwise, will be presented in subject data listings.

The number and percentage of subjects with TEAEs will be calculated from the following viewpoints.

- All/Treatment-related Treatment-Emergent Adverse Events by System Organ Class and Preferred Term
- All/Treatment-Emergent Adverse Events by Preferred Term in Decreasing Frequency
- All/Treatment-Emergent Adverse Events by System Organ Class, Preferred Term, and CTCAE Grade
- All/Treatment-Emergent Serious Adverse Events by System Organ Class, Preferred Term
- All/Treatment-Emergent Adverse Events Leading to Death by System Organ Class and Preferred Term
- All/Treatment-Emergent Adverse Events Leading to Study Drug Withdrawal by System

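### SAP 5.6.2 gives new AEs a 37-day post-dose window but re-emerged and worsened AEs only an undefined treatment period, and does not end the window when collection closes early for new anti-tumour therapy

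*Protocol*

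**What the plan says.** **Definition of a TEAE.** SAP 5.6.2 has three limbs.

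- An AE absent at baseline counts if it "emerged during time from the first dose of study drug to 37 days after" the subject's last dose.
- An AE that was present before treatment and had stopped counts if it returns during treatment.
- A continuing AE counts if it "Worsened in severity during treatment relative to the pretreatment state, when the AE was continuous".

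Only treatment-emergent AEs enter the summary tables. All AEs are listed. Protocol 9.7.1.8.2 uses *during treatment* for all three limbs and gives no number of days. SAP Section 7, which lists changes from the protocol's planned analyses, does not mention the 37 days.

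**Collection.** Protocol 9.1.1.3 places final observation 30 days (+7) after the last dose, or at the start of new anti-tumour therapy if that is earlier. Under protocol 9.5.1.5.1 AEs are recorded through that visit, and "SAEs will be collected until the final observation visit". If other anti-tumour therapy is needed within 30 days of the last dose, the visit must come first. Footnote b of Table 5 adds that "the data within 7 days before next anti-tumor therapy can be used for final observation".

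**Exceptions.** Related SAEs (protocol 9.5.4.1) and related events of interest (9.5.4.3.2) are reportable without time limit. SAEs already open are followed to resolution or stabilization.

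**The concern.** The SAP rewrote one limb of the protocol's definition and left the other two. The same clinical event on the same post-dose day is therefore tabulated or not according to whether a milder form was recorded at baseline.

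Cytopenias make this more than a drafting point. Protocol Table 1 shows treatment-related thrombocytopenia in 19 of 151 B-cell NHL subjects (13%), and protocol 7.4.2.2 reports it in 3 of 7 subjects in the Japanese Phase 1 study. Patients may enter this study with hemoglobin as low as 9.0 g/dL. Some will therefore carry a baseline cytopenia that can only worsen, not newly emerge.

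The second issue is that the 37-day limit is written as if every subject were observed to the end of it. Subjects who start new therapy early are not. SAP 5.3.5 imputes nothing, so an event that is not collected is counted as no event. Protocol 9.5.1.5.1 links early therapy to deterioration in the subject's condition, so the shortened observation may not fall at random. A reader of the TEAE, SAE and fatal-TEAE tables would not know how much of the window lies behind them.

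**Working it through.** **1. Where the 37 days comes from.** Latest final observation = 30 + 7 = 37 days after the last dose. This reproduces the SAP figure. For a subject with no new therapy within 30 days, the window ends on the latest day the visit may occur, so there is no general mismatch between window and collection.

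**2. The three limbs side by side.**

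| Limb | Protocol 9.7.1.8.2 | SAP 5.6.2 |
|---|---|---|
| Absent at baseline | during treatment | first dose to last dose + 37 days |
| Stopped before treatment, then returned | during treatment | during treatment |
| Continuous, then worse | during treatment | during treatment |

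Take two subjects with Grade 4 thrombocytopenia reported as an AE ten days after the last dose (an illustration). Subject A had none at baseline: 10 is within 37, so the event is a TEAE. Subject B had a low-grade thrombocytopenia recorded at baseline: the event is a worsening after the last dose, so on a literal reading it is not a TEAE. The serious and fatal tables are restricted to treatment-emergent events and inherit the difference.

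**3. Observation after early closure.** If new therapy starts on Day d after the last dose (d up to 30), routine collection has closed by Day d. Days of the window not routinely observed are at least 37 − d, a share of (37 − d)/37.

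| d (assumed) | 37 − d | Share of window |
|---|---|---|
| 7 | 30 | 81% |
| 14 | 23 | 62% |
| 21 | 16 | 43% |
| 28 | 9 | 24% |

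**4. Across a cohort.** Suppose a share f of subjects start new therapy on Day 14 and the rest are observed to Day 37. The post-dose person-time lost is f × 23/37. At f = 25% this is 0.25 × 0.622 = 16%; at f = 75% it is 0.75 × 0.622 = 47%. Both f and the day are assumptions. These are shares of observation time, not of events.

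**5. What escapes routine capture after early closure.** Related SAEs, related events of interest and the outcome of open SAEs still reach the sponsor. What remains is non-serious AEs (including related ones, apart from events of interest) and new SAEs judged unrelated. The SAP does not say whether related SAEs reported after final observation enter the TEAE tables.

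**The case against.** *Early closure is deliberate.* It is stated consistently in the protocol (9.1.1.3, 9.5.1.5.1 and Table 5), and it keeps the next regimen's toxicity out of the counts. It applies only when therapy is needed within 30 days. This stands: collecting SAEs past new therapy would be a design choice, not a correction. The SAP's silence on where the window ends for these subjects remains.

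*The 37 days may be meant for all three limbs.* Because *during treatment* is undefined, it could be read as the same window. That is possible, but the text does not say so, and a programmer following it could go either way.

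*Late cytopenias are not hidden.* SAP 5.6.3 tabulates markedly abnormal laboratory values for the study overall with no such limit, hematology is drawn at discontinuation and final observation, and every AE is listed. An eligible but low count need not have been recorded as a baseline AE, so a later event could qualify as new. All true. This limits the damage to the TEAE, SAE and fatal-TEAE tables, where the inconsistency still operates.

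*The omission from SAP Section 7 is minor.* The protocol leaves analysis detail to the SAP, and 37 days restates a visit window. It is minor, but it costs one line.

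Four stronger readings are tempting, and the documents do not support them.

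- *Deaths are undercounted.* The gap is confined to deaths from new, unrelated events after early closure. Worsening lymphoma is recorded as progression, not as an AE.
- *Cohort 2 is biased against cohort 1.* No statistical comparison is planned (SAP 5.3.3), and nothing gives the rate of early therapy by cohort. The 13 planned DLBCL subjects are an efficacy-evaluable target, not the Safety Analysis Set on which these rates are based.
- *Final observation can predate the last dose.* Footnote b lets recent data serve for the visit. It does not say that AE recording stops before the last dose.
- *SAE collection must run to Day 30 regardless of new therapy.* This would still leave Days 31 to 37 of the SAP window uncollected.

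**Conclusion.** The SAP's definition of treatment-emergence is internally inconsistent and should be corrected. Its first limb runs to 37 days after the last dose. The other two rest on an undefined term that, read literally, ends with treatment. Separately, the 37-day window is not fully observed in subjects who start other anti-tumour therapy within 30 days, and the SAP does not end the window there.

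The unobserved share for such a subject is at least 24% to 81% of the window for new therapy between Day 28 and Day 7, with those days assumed. How many subjects are affected, and how many events are missed, cannot be computed from the documents. The finding is that events can be left out of the tables by rule or by early closure. That the reported rates are in fact too low is not shown.

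**What to change.** All changes are in the SAP.

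1. **5.6.2:** apply one window to all three limbs (new, re-emerged, worsened), from first dose to the earlier of 37 days after the last dose and the start of new anti-tumour therapy.
2. **5.6.2:** state that related SAEs reported after final observation, with onset within 37 days of the last dose, are tabulated and flagged as before or after new therapy. Those after it lie outside the window in item 1, so the flag must keep them distinguishable.
3. **Safety tables:** report how many subjects closed early for new therapy, and on which day after the last dose.
4. **Section 7:** list the change from protocol 9.7.1.8.2.

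The cost is a few lines of text, a revised TEAE flag and one short table. One thing to check first: protocol 9.4.7 records therapies up to final observation, which by rule comes before the new therapy, so its start date may not be on the CRF for every subject. SAP 5.4.2 already needs such dates for censoring PFS. Where a date is missing, the date of final observation can mark the end of the window.

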9.5.1.5.2 SERIOUS ADVERSE EVENTS AND EVENTS ASSOCIATED WITH SPECIAL SITUATIONS

An SAE is any untoward medical occurrence that at any dose:

• Results in death

Eisai Confidential Page 47 of 71

- Is life-threatening (ie, the subject was at immediate risk of death from the adverse event as it occurred; this does not include an event that, had it occurred in a more severe form or was allowed to continue, might have caused death)
- Requires inpatient hospitalization or prolongation of existing hospitalization
- Results in persistent or significant disability/incapacity
- Is a congenital anomaly/birth defect (in the child of a subject who was exposed to the study drug)

Other important medical events that may not be immediately life-threatening or result in death or hospitalization but, when based on appropriate medical judgment, may jeopardize the subject or may require intervention to prevent one of the outcomes in the definition of SAE listed above should also be considered SAEs. Medical and scientific judgment should be exercised in deciding whether expedited reporting is appropriate in such situations.

For this study, occurrence of T-cell lymphoblastic lymphoma/T-cell acute lymphoblastic leukemia or myeloid malignancy including myelodysplastic syndrome will be considered AEs of interest for this study. These events should be reported to the sponsor by completed SAE report (see Section 9.5.4.3.2) and considered as serious only if events meet the serious criteria. These AEs should be entered on the CRF even if the events do not meet serious criteria. If subject experiences T-cell lymphoblastic lymphoma/T-cell acute lymphoblastic leukemia, enrollment of subject should be discontinued.

In addition to the above, events associated with special situations include pregnancy or exposure to study drug through breastfeeding; AEs associated with study drug overdose, misuse, abuse, or medication error (see Sections 9.5.4.2 and 9.5.4.3). These events associated with special situations are to be captured using the SAE procedures but are to be considered as SAEs only if they meet one of the above criteria. All AEs associated with special situations are to be reported on the CRF whether or not they meet the criteria for SAEs.

All SAEs must be followed to resolution or, if resolution is unlikely, to stabilization.

The following hospitalizations are not considered to be SAEs because there is no "adverse event" (ie, there is no untoward medical occurrence) associated with the hospitalization:

- Hospitalizations for respite care
- Planned hospitalizations required by the protocol
- Hospitalization planned before informed consent (where the condition requiring the hospitalization has not changed after study drug administration)
- Hospitalization for administration of study drug or insertion of access for administration of study drug
- Hospitalization for routine maintenance of a device (eg, battery replacement) that was in place before study entry

Eisai Confidential Page 48 of 71 FINAL: 29 Jan 2021

Eisai Confidential Page 49 of 167

9.5.1.5.3 LABORATORY MEASUREMENTS

Clinical laboratory tests to be performed, including hematology, chemistry, and urinalysis, are summarized in Table 4. The Schedule of Procedures/Assessments (Table 5) shows the visits and time points at which blood for clinical laboratory tests and urine for urinalysis will be collected in the study. Clinical laboratory tests will be performed at each site.

Table 4 Clinical Laboratory Tests

Category	Parameters
Hematology	WBC count with differential (basophils, eosinophils, lymphocytes, monocytes, neutrophils), RBC count, hemoglobin, hematocrit, and platelets Peripheral blood smear morphology assessment ^a
Chemistry	
Liver function tests	AST, ALT, ALP, total bilirubin, direct bilirubin
Renal function tests	Creatinine, BUN
Other	Total protein, albumin, LDH, creatine phosphokinase, amylase, uric acid, glucose, triglycerides, cholesterol, sodium, chloride, potassium, calcium, phosphorus, INR ^b
Urinalysis	Protein (qualitative), glucose (qualitative), occult blood

ALP = alkaline phosphatase, ALT = alanine aminotransferase, AST = aspartate aminotransferase, BUN = blood urea nitrogen, INR = international normalized ratio, LDH = lactate dehydrogenase, RBC = red blood cell, WBC = white blood cell.

For the management of clinically significant laboratory abnormalities, refer to the Tazemetostat Dose Reduction and Interruption Instructions in Table 2.

A laboratory abnormality may meet the criteria to qualify as an AE as described in this protocol (see Section 9.5.1.5.1). In these instances, the AE corresponding to the laboratory abnormality will be recorded on the CRF.

